  - 6) Non-neoplastic diseases (psoriasis vulgaris, secondary polycythemia, hemolytic anemia)
  - 7) Rhabdomyolysis
  - 8) Hypothyroidism
  - 9) Polycystic kidney
  - 10) Lead poisoning/lead nephropathy
  - 11) Down's syndrome
  - 12) Familial juvenile gouty nephropathy
  - 13) Hyperlactacidemia
  - 14) Glycogen storage disease type 1

6. A prolonged QTcF interval (QTcF >450 ms) as demonstrated by a repeated 12-lead electrocardiogram (ECG)
7. Prohibited concomitant drugs within 14 days prior to screening and during the study
8. Changing the dosage and/or administration, or initiating any restricted concomitant drugs within 14 days prior to screening and during the study
9. Have been routinely receiving non-steroidal anti-inflammatory drugs (NSAIDs) or corticosteroids (not including topical application) for a disease other than gouty arthritis
10. Comorbidities with nephrolithiasis or clinical urinary calculi (eg, haematuria, back pain)
11. Evidence of clinically significant disease (eg, cardiac disease: heart failure and angina unstable, respiratory, gastrointestinal, renal, or neurological disease: cerebral infarction) that in the opinion of the investigator(s) could affect the subject's safety or interfere with the study assessments
12. Relevant history of cardiac (eg, myocardial infarction or angina attacks) or neurologic disease (eg, cerebral infarction) within 1 year prior to screening
13. Current presence of active gastrointestinal ulcer disease, or history of active gastrointestinal ulcer disease within 1 year prior to screening
14. Evidence of clinical significant hepatic disease: refer to Grade 2 in the "Seriousness Grading Criteria for Adverse Drug Reactions" or AST (GOT) or ALT (GPT) >3× upper limit of normal (ULN) in the Screening Phase
15. Estimated glomerular filtration rate (eGFR) of <30 mL/min/1.73 m^2 in the Screening Phase
16. Systolic blood pressure of ≥180 mmHg or diastolic blood pressure of ≥110 mmHg in the Screening Phase
17. HbA1c (NGSP value) of ≥8.4% in the Screening Phase
18. Current presence or history of neoplasm malignant in the 5 years prior to screening
19. Hypersensitivity to the study drugs (dotinurad or febuxostat) or their excipients, or all of urine alkalinizer (potassium citrate/sodium citrate hydrate compound preparations, et al)
20. Any history of or concomitant medical condition that in the opinion of the investigator(s) would compromise the subject's ability to safely complete the study

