#### 7.1.1.1 Current Treatment and Unmet Medical Needs

The etiology of hyperuricemia includes excessive production of uric acid, decreased excretion of uric acid, and the combined type. Approximately 90% of hyperuricemia is the uric acid decreased excretion type and the combined type in China (Chen, 2006).

The basic principle of selecting drug is based on classification of hyperuricemia. The xanthine oxidase inhibitor allopurinol has been used as a uric acid production inhibitor for many years; febuxostat is marketed later, and has been increasingly prescribed in recent years, but hepatic dysfunction, the incidence of cardiovascular death and all-cause mortality was reported to be high. Benzbromarone is the main uricosuric drug, but it can cause serious hepatic disorders (Van der Klauw, et al., 1994). It also has a potent inhibitory effect on the drug metabolizing enzyme cytochrome P450 (CYP), particularly on CYP2C9 (Kunishima, et al., 2003; Locuson, et al., 2003). So a potent, well-tolerated, and selective uricosuric drug without causing hepatic impairment, and less drug-drug interaction is needed in clinical practice.

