  - 6) Non-neoplastic diseases (psoriasis vulgaris, secondary polycythemia, hemolytic anemia)
  - 7) Rhabdomyolysis
  - 8) Hypothyroidism
  - 9) Polycystic kidney
  - 10) Lead poisoning/lead nephropathy
  - 11) Down's syndrome
  - 12) Familial juvenile gouty nephropathy
  - 13) Hyperlactacidemia
  - 14) Glycogen storage disease type 1
6. A prolonged QTcF interval (QTcF >450 ms) as demonstrated by a repeated 12-lead electrocardiogram (ECG)
7. Prohibited concomitant drugs within 14 days prior to screening and during the study
8. Changing the dosage and/or administration, or initiating any restricted concomitant drugs within 14 days prior to screening and during the study
9. Have been routinely receiving non-steroidal anti-inflammatory drugs (NSAIDs) or corticosteroids (not including topical application) for a disease other than gouty arthritis
10. Comorbidities with nephrolithiasis or clinical urinary calculi (eg, haematuria, back pain)
11. Evidence of clinically significant disease (eg, cardiac disease: heart failure and angina unstable, respiratory, gastrointestinal, renal, or neurological disease: cerebral infarction) that in the opinion of the investigator(s) could affect the subject's safety or interfere with the study assessments
12. Relevant history of cardiac (eg, myocardial infarction or angina attacks) or neurologic disease (eg, cerebral infarction) within 1 year prior to screening
13. Current presence of active gastrointestinal ulcer disease, or history of active gastrointestinal ulcer disease within 1 year prior to screening

14. Evidence of clinical significant hepatic disease: refer to Grade 2 in the “Seriousness Grading Criteria for Adverse Drug Reactions” or AST (GOT) or ALT (GPT)  $>3\times$  upper limit of normal (ULN) in the Screening Phase
15. eGFR of  $<30$  mL/min/1.73 m^2 in the Screening Phase
16. Systolic blood pressure of  $\geq 180$  mmHg or diastolic blood pressure of  $\geq 110$  mmHg in the Screening Phase
17. HbA1c (NGSP value) of  $\geq 8.4\%$  in the Screening Phase
18. Current presence or history of neoplasm malignant in the 5 years prior to screening
19. Hypersensitivity to the study drugs (dotinurad or febuxostat) or their excipients, or all of urine alkalinizer (potassium citrate/sodium citrate hydrate compound preparations, et al)
20. Any history of or concomitant medical condition that in the opinion of the investigator(s) would compromise the subject’s ability to safely complete the study

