#### 9.5.5 Completion/Discontinuation of Subjects

A subject may elect to discontinue the study at any time for any reason. Wherever possible, all subjects who discontinue the study are to complete the study's early discontinuation procedures indicated in the Schedule of Procedures/Assessments ([Table 3](#)).

Subjects who meet any of the following criteria will be discontinued from the study:

1. Subjects who withdrew consent
2. Subject choice (eg, change in residence)
3. Subjects who had AEs leading to discontinuation from the study
4. Subjects who were considered impossible to continue the study due to progression of gout or inadequate therapeutic effect of the study drug by the investigator
5. Subjects who take prohibited concomitant drugs during the study, and the use is considered to interfere with the efficacy assessments and affect the subject's safety by the investigator, following consultation with the sponsor
6. Subjects who change the dosage and/or administration, or initiate any restricted concomitant drugs during the study, and the change or initiation is considered to interfere with the efficacy assessments and affect the subject's safety by the investigator, following consultation with the sponsor
7. Subjects who begin to routinely receive NSAIDs or corticosteroids (not including topical application) for a disease other than gouty arthritis
8. Subjects who developed gouty arthritis attack after the randomization day and before taking the first study drug
9. Subjects who developed gouty arthritis at Week 4 or 12, and the gouty arthritis did not disappear within 1 week after the specified visit date of Week 4 or 12
10. Subjects who developed nephrolithiasis (including clinical urinary calculi) after the first study treatment (excluding at the final visit)

11. Subjects who developed acute kidney injury (AKI) after the first study treatment (excluding at the final visit)

AKI is defined as any of the following (Kidney Disease: Improving Global Outcomes [KDIGO] 2012):

- Increase in serum creatinine (SCr) by  $\geq 0.3$  mg/dL ( $\geq 26.5$   $\mu$ mol/L) within 48 hours; or
- Increase in SCr to  $\geq 1.5$  times baseline, which is known or presumed to have occurred within the prior 7 days; or
- Urine volume  $<0.5$  mL/kg/h for 6 hours

12. Subjects with SUA level of  $\leq 2.0$  mg/dL for 2 consecutive visits (excluding at the final visit)

13. Subjects with AST or ALT level of  $5 \times$  ULN (excluding at the final visit)

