#### 4.6.3 Laboratory Values

Laboratory results will be summarized using Système International (SI) units, as appropriate. For all quantitative parameters listed in protocol Section 9.5.1.4.4, the actual value and the change from baseline to each postbaseline visit will be summarized by visit and treatment group using descriptive statistics. Qualitative parameters listed in protocol Section 9.5.1.4.4 will be summarized using frequencies (number and percentage of subjects), and changes from baseline to each postbaseline visit will be reported using shift tables. Percentages will be based on the number of subjects with both nonmissing baseline and relevant postbaseline results.

Laboratory test results will be assigned a low/normal/high (LNH) classification according to whether the value was below (L), within (N), or above (H) the laboratory parameter's reference range. Within-treatment comparisons for each laboratory parameter will be based on 3-by-3 tables (shift tables) that compare the baseline LNH classification to the LNH classification at each postbaseline visit. Similar shift tables will also compare the baseline LNH classification to the LNH classification for the highest and lowest value.

[Appendix 1](#) (Sponsor's Grading for Laboratory Values) presents the criteria that will be used to identify subjects with treatment-emergent markedly abnormal laboratory values (TEMAVs). A TEMA V is defined as a postbaseline value with an increase from baseline to a grade of 2 or higher. When displaying the incidence of TEMA Vs, each subject may be counted once in the laboratory parameter high and in the laboratory parameter low categories, as applicable.

The number (percentage) of subjects with TEMA V (markedly abnormal high/low) will be summarized by treatment group.

The number (percentage) of subjects who met the following criteria for the hepatic test at the same time will be summarized by treatment group. If a subject met the criteria more than once for available laboratory data, the subject will be counted only once in the calculation of the incidence.

- Elevated AST or ALT lab value that is greater than or equal to  $3 \times$  ULN
- Elevated total bilirubin lab value that is greater than or equal to  $2 \times$  ULN
- Alkaline phosphatase lab value that is less than  $2 \times$  ULN

A subject data listing of laboratory values will be provided.

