## Appendix 1      Sponsor's Grading for Laboratory Values

	Grade 1	Grade 2	Grade 3	Grade 4
BLOOD/BONE MARROW				
Hemoglobin	<LLN – 10.0 g/dL <LLN – 100 g/L <LLN – 6.2 mmol/L	<10.0 – 8.0 g/dL <100 – 80 g/L <6.2 – 4.9 mmol/L	<8.0 g/dL <80 g/L <4.9 mmol/L	
Leukocytes (total WBC)	<LLN – 3.0×10  /L <LLN – 3000/mm 	<3.0 – 2.0×10  /L <3000 – 2000/mm 	<2.0 – 1.0×10  /L <2000 – 1000/mm 	<1.0×10  /L <1000/mm 
Lymphocytes	<LLN – 800/mm  <LLN – 0.8×10  /L	<800 – 500/mm  <0.8 – 0.5×10  /L	<500 – 200/mm  <0.5 – 0.2×10  /L	<200/mm  <0.2×10  /L
Neutrophils	<LLN – 1.5×10  /L <LLN – 1500/mm 	<1.5 – 1.0×10  /L <1500 – 1000/mm 	<1.0 – 0.5×10  /L <1000 – 500/mm 	<0.5×10  /L <500/mm 
Platelets	<LLN – 75.0×10  /L <LLN – 75,000/mm 	<75.0 – 50.0×10  /L <75,000 – 50,000/mm 	<50.0 – 25.0×10  /L <50,000 – 25,000/mm 	<25.0×10  /L <25,000/mm 
METABOLIC/LABORATORY				
Albumin, serum- low (hypoalbuminemia)	<LLN – 3 g/dL <LLN – 30 g/L	<3 – 2 g/dL <30 – 20 g/L	<2 g/dL <20 g/L	
Alkaline phosphatase	>ULN – 2.5×ULN if baseline was normal; 2.0 – 2.5×baseline if baseline was abnormal	>2.5 – 5.0×ULN if baseline was normal; >2.5 – 5.0×baseline if baseline was abnormal	>5.0 – 20.0×ULN if baseline was normal; >5.0 – 20.0×baseline if baseline was abnormal	>20.0×ULN if baseline was normal; >20.0×baseline if baseline was abnormal
ALT	>ULN – 3.0×ULN if baseline was normal; 1.5 – 3.0×baseline if baseline was abnormal	>3.0 – 5.0×ULN if baseline was normal; >3.0 – 5.0×baseline if baseline was abnormal	>5.0 – 20.0×ULN if baseline was normal; >5.0 – 20.0×baseline if baseline was abnormal	>20.0×ULN if baseline was normal; >20.0×baseline if baseline was abnormal
AST	>ULN – 3.0×ULN if baseline was normal; 1.5 – 3.0×baseline if baseline was abnormal	>3.0 – 5.0×ULN if baseline was normal; >3.0 – 5.0×baseline if baseline was abnormal	>5.0 – 20.0×ULN if baseline was normal; >5.0 – 20.0×baseline if baseline was abnormal	>20.0×ULN if baseline was normal; >20.0×baseline if baseline was abnormal

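### Subjects entering with raised ALT or AST can reach 5×ULN without counting as markedly abnormal; a by-arm count in multiples of ULN would close the gap cheaply

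*SAP*

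**What the plan says.** SAP 4.6.3 (Laboratory Values) counts a TEMAV when a result "is defined as a postbaseline value with an increase from baseline to a grade of 2 or higher" on the sponsor's grading in Appendix 1. For ALT and AST that grading has two scales.

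- Normal baseline: Grade 2 is ">3.0 – 5.0×ULN if baseline was normal".
- Abnormal baseline: Grade 1 is "1.5 – 3.0×baseline if baseline was abnormal" and Grade 2 is ">3.0 – 5.0×baseline if baseline was abnormal". No ULN limit is attached.

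The protocol's Appendix 1 has the same ALT and AST grades. Both appendices state that they are based on CTCAE version 5.0.

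Two protocol rules use multiples of ULN. Exclusion criterion 14 bars "AST (GOT) or ALT (GPT) >3× upper limit of normal (ULN) in the Screening Phase". Discontinuation criterion 13 in section 9.5.5 covers "Subjects with AST or ALT level of" 5×ULN, except at the final visit.

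SAP 4.6.3 also plans descriptive values and changes by visit, low/normal/high shift tables (including highest and lowest value), a combined hepatic count and a listing. The combined count requires ALT or AST ≥3×ULN, total bilirubin ≥2×ULN and alkaline phosphatase <2×ULN at the same time.

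**The concern.** A baseline-relative scale measures change in subjects who start high, but it says little about how high they end up. A subject admitted with raised enzymes can reach a level that the protocol treats as a reason for discontinuation and still be Grade 1 in the TEMAV table. The same value from a normal baseline would be counted.

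The other laboratory tables do not show it either. A raised baseline that rises further stays high-to-high in the shift tables, whether it ends at 2×ULN or 8×ULN. The combined hepatic count leaves out an isolated ALT or AST rise. Visit means can hide individual outliers, and a listing gives no incidence by arm.

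The liver is of interest in this comparison. Protocol 7.1.1.1 describes the need for a "selective uricosuric drug without causing hepatic impairment", among other properties, and reports hepatic dysfunction with febuxostat, the comparator. Liver injury is a study-specific adverse event (protocol 9.5.1.4.3) and a TEAE of interest (SAP 4.6.2). A reader of the report will want to know how many subjects in each arm passed 3×ULN and 5×ULN, and no planned table gives that for subjects with raised baselines.

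**Working it through.** The plan states no figure of its own here to reproduce; the check is threshold arithmetic.

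**Inputs**
- TEMAV: grade rises to 2 or more (SAP 4.6.3).
- Abnormal baseline: Grade 2 starts above 3.0×baseline (SAP Appendix 1).
- Normal baseline: Grade 2 starts above 3.0×ULN and Grade 3 above 5.0×ULN (SAP Appendix 1).
- Highest ALT or AST at entry: 3.0×ULN (protocol exclusion 14, stated figure).
- Criterion 13 level: 5×ULN (protocol 9.5.5). No inequality sign is printed; the result holds under ≥ or >.
- Baseline: last value before first dose (SAP section 7). Protocol Table 3 schedules laboratory tests at screening and none at Visit 2, so baseline will usually be the screening value to which the entry limit applies.

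**Formula.** Let b be the baseline and v the later value, both in ×ULN, with 1 < b ≤ 3. Grade 2 starts above 3b. A value is at or above 5×ULN and still not a TEMAV when 5 ≤ v ≤ 3b, which requires b ≥ 5/3 = 1.67.

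| Baseline (×ULN) | Grade 2 starts above (×ULN) | At or above 5×ULN but not a TEMAV |
|---|---|---|
| 1.0 or less | 3.0 | none |
| 1.2 | 3.6 | none |
| 1.5 | 4.5 | none |
| 1.67 | 5.0 | 5.0 only |
| 2.0 | 6.0 | 5 to 6 |
| 2.5 | 7.5 | 5 to 7.5 |
| 3.0 | 9.0 | 5 to 9 |

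**Example.** Baseline 2.0, later value 5.5: 5.5/2.0 = 2.75×baseline, Grade 1, not a TEMAV. From a normal baseline, 5.5×ULN is Grade 3 and a TEMAV.

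**Bilirubin.** With an abnormal baseline, Grade 2 starts above 1.5×baseline (SAP Appendix 1). A value of 2×ULN is then uncounted when b ≥ 2/1.5 = 1.33.

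**What other outputs catch.** Protocol 9.5.1.4.1 makes a laboratory abnormality an adverse event if it leads to an intervention or to withdrawal or withholding of study drug. A subject discontinued under criterion 13 should therefore appear in TEAEs leading to withdrawal (SAP 4.6.2) and in disposition (SAP 4.2.2), and possibly in the Hepatic disorders SMQ summary. Two groups are not reliably caught:
- final-visit values, since criterion 13 exempts them; for completers in the dotinurad arm this visit follows the 12-week 4 mg period;
- isolated rises that lead to no action, whose classification as an adverse event is left to the investigator. Liver injury must always be reported, but section 9.5.1.4.3 gives no enzyme threshold for it.

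**Size.** The documents do not give the share entering at or above 1.67×ULN. Purely as an illustration, an assumed 3% to 8% of 225 per arm is 6.75 to 18, or about 7 to 18 subjects graded on the affected part of the scale. If 2% to 10% of those (also assumed) had a value between 5×ULN and 3×baseline, that is 6.75 × 0.02 = 0.1 to 18 × 0.10 = 1.8 subjects per arm.

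**The case against.** The strongest reply is that nothing is wrong with the scale. TEMAV means treatment-emergent, so grading an abnormal baseline against itself is a sensible choice. It follows the stated CTCAE basis and is the same in protocol and SAP. Criterion 13 governs individual subjects while the TEMAV table is a descriptive summary, and nothing requires them to share a threshold. This stands: a reader might infer that the two contradict each other, and they do not.

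A reader might also infer that subjects withdrawn for liver enzymes vanish from the report. The adverse-event and disposition rules above do not support that.

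Nor is the combined hepatic count the only liver output tied to ULN. The TEMAV scale uses ULN for normal baselines, and the shift tables use the reference range. What is missing is a count in multiples of ULN, without the bilirubin and alkaline phosphatase conditions, for raised baselines.

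It would likewise go too far to call hepatic safety the reason for developing the drug. Protocol 7.1.1.1 lists it beside potency, tolerability, selectivity and fewer drug interactions.

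The affected range may also be narrower than 1.67 to 3×ULN. Exclusion 14 has a second limb, "Evidence of clinical significant hepatic disease: refer to Grade 2 in the" named grading scheme, whose thresholds are not in the documents, and other exclusions may remove more subjects. Just above 1.67×ULN the gap is trivial: at 1.7×ULN, Grade 2 starts at 5.1×ULN.

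Finally, SAP section 2 and SAP 4.8 allow additional analyses, so the count could be produced later. But a prespecified table carries more weight than one added after unblinding.

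**Conclusion.** This is a cheap improvement, not an error in the grading. The documents' own thresholds show that a subject entering at about 1.67×ULN or more can reach 5×ULN without counting as a TEMAV, and that no other planned laboratory table shows an isolated rise of this kind by arm. The practical gap is final-visit values and elevations that led to no action, in subjects with raised baselines.

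The number affected is unknown and probably small. The illustration of 0.1 to 1.8 subjects per arm rests wholly on assumed shares. The conclusion also assumes that subjects in the affected range are enrolled despite the other exclusions. Subjects with a normal baseline are always flagged once they pass 5×ULN, as are those whose abnormal baseline lies below 1.67×ULN. The primary efficacy analysis is unaffected.

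**What to change.** In SAP 4.6.3, add to the hepatic summary the number (%) of subjects per arm with:

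- any post-baseline ALT or AST ≥3×ULN;
- any post-baseline ALT or AST ≥5×ULN;
- any post-baseline total bilirubin ≥2×ULN.

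Count these regardless of baseline grade, include final-visit values, and split each row by normal or raised baseline. Keep the TEMAV table, with a footnote that ALT, AST and bilirubin are graded in multiples of baseline when baseline is abnormal.

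The cost is one table from central-laboratory data already collected, with no change to any clinical rule. SAP section 2 allows such an update before unblinding. The downside is that subjects who enter near 3×ULN may cross it by chance; the baseline split makes those crossings visible.

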#### 4.6.4 Vital Signs

Descriptive statistics for vital signs parameters (ie, systolic and diastolic BP, pulse and temperature) and weight, and changes from baseline will be presented by visit and treatment group. Analysis of changes from baseline will be based on the number of subjects with both nonmissing baseline and relevant postbaseline results.

The number (percentage) of subjects with at least 1 postbaseline clinically notable values in vital signs and weight will be summarized by treatment group. Clinically notable values will be defined in the [Table 1](#). A subject data listing of vital signs and weight will be provided.

**Table 1** **Vital Sign Criteria**

Variable	Criterion value a	Change relative to baseline a	Clinically notable range
Pulse	> 120 bpm	Increase of $\geq 15$ bpm	H
	< 50 bpm	Decrease of $\geq 15$ bpm	L
Systolic BP	> 180 mmHg	Increase of $\geq 20$ mmHg	H
	< 90 mmHg	Decrease of $\geq 20$ mmHg	L
Diastolic BP	> 105 mmHg	Increase of $\geq 15$ mmHg	H
	< 50 mmHg	Decrease of $\geq 15$ mmHg	L
Weight	--	Increase of $\geq 7\%$	H
	--	Decrease of $\geq 7\%$	L

BP = blood pressure, H = high, L = low.

a Clinically notable means that a value must meet the criterion value and must attain the specified magnitude of change relative to baseline.

#### 4.6.5 Electrocardiograms

Descriptive statistics for ECG parameters (QTcF, QT, PR, QRS, RR and heart rate) and changes from baseline will be presented by visit and treatment group.

Shift tables will present changes from baseline in ECG interpretation (categorized as normal; abnormal, not clinically significant; and abnormal, clinically significant) by visit and treatment group.

In addition, the number (percentage) of subjects with at least 1 postbaseline abnormal ECG result in QTcF will be summarized. Clinically abnormal ECG results in QTcF will be categorized as follows:

Absolute QTcF interval prolongation:

- QTcF interval >450 ms
- QTcF interval >480 ms
- QTcF interval >500 ms

Change from baseline in QTcF interval:

- QTcF interval increases from baseline >30 ms
- QTcF interval increases from baseline >60 ms

A subject data listing of ECG results will be provided.

#### 4.6.6 Other Safety Analyses

No analyses are planned for pregnancy tests, and abdominal ultrasound and plain abdominal radiography.

A subject data listing of urinary calculi on abdominal ultrasound/abdominal radiography will be provided.

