#### 9.5.1.4.3 STUDY-SPECIFIC ADVERSE EVENTS

The study-specific events, gouty arthritis, urinary calculi, acute renal failure, liver injury, should always be considered adverse events and reported on the Adverse Event CRF. As for the diagnosis of gouty arthritis, refer to [Section 9.4.7.4](#). In addition, site(s) of onset of gouty arthritis should be collected as additional information and included in the AE term.

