### **Abdominal Ultrasound/Abdominal Radiography**

Abdominal ultrasound and plain abdominal radiography will be performed at the Screening Visit and Week 24/Early Termination Visit ([Table 3](#)), and the presence or absence of urinary calculi or clinically significant urinary calculi will be observed. Documentation of the abdominal ultrasound and plain abdominal radiography will be included in the source documentation at the site. Clinically significant abnormal findings that meet the definition of an AE from the abdominal ultrasound and plain abdominal radiography will be reported on the Adverse Events CRF.

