#### 9.7.1.8.6 OTHER SAFETY ANALYSES

No analyses are planned for pregnancy tests, and abdominal ultrasound and plain abdominal radiography specified in [Section 9.5.1.4.8 Other Safety Assessments](#).

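### Scheduled stone imaging is listed but not counted by arm, so the urinary-calculi summary depends on which imaging findings sites record as adverse events

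*SAP*

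**What the plan says.** **Imaging.** Protocol 9.5.1.4.8 and Table 3 schedule it at entry and exit: "Abdominal ultrasound and plain abdominal radiography will be performed at the Screening Visit and Week 24/Early Termination Visit". Its purpose is that "the presence or absence of urinary calculi or clinically significant urinary calculi will be observed". On where the result is kept, the same section says: "Documentation of the abdominal ultrasound and plain abdominal radiography will be included in the source documentation at the site".

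**Adverse event recording.** Two places bear on a stone found by imaging.
- Protocol 9.5.1.4.3: "The study-specific events, gouty arthritis, urinary calculi, acute renal failure, liver injury, should always be considered adverse events". These events are to go on the Adverse Event CRF.
- Protocol 9.5.1.4.8: "Clinically significant abnormal findings that meet the definition of an AE from the abdominal ultrasound and plain abdominal radiography will be reported" on the adverse event page.

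**Analysis.** SAP 4.6.6 says "No analyses are planned for pregnancy tests, and abdominal ultrasound and plain abdominal radiography", and Protocol 9.7.1.8.6 agrees: "No analyses are planned for pregnancy tests, and abdominal ultrasound and plain abdominal radiography specified in" the section on other safety assessments. SAP 4.6.6 then adds a subject listing of calculi seen on imaging. The only planned summary of calculi by treatment group is in SAP 4.6.2, among the events of interest, defined by the MedDRA group Urolithiases. SAP 4.6 makes all safety analysis descriptive, without hypothesis tests.

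**The concern.** The protocol treats stones as a risk worth watching. They are one of four study-specific events. Existing nephrolithiasis is an exclusion (9.3.2, item 10), and urinary tract management has its own section (9.4.7.3). The mechanism makes the between-arm comparison relevant: dotinurad blocks renal reabsorption of uric acid (7.1.2), while febuxostat is classed as a production inhibitor (9.4.7.1).

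The scheduled look for stones is not what gets counted by arm. The counted quantity is stones recorded as adverse events, and for a stone without symptoms that step rests on how the site reads two passages. Two sites could both believe they are compliant and record the same finding differently. A listing shows individual cases but gives neither a by-arm count nor the number of subjects imaged.

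At stake is the completeness of one named safety summary. No error rate or efficacy conclusion is involved.

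**Working it through.** The plan states no figure for calculi, so there is none to reproduce on this point. Its only computed design figure is about 90% power for the responder comparison. With 225 per arm, 45% v 60% and two-sided 0.05, power = Φ[(0.15·√225 − 1.96·√(2·0.525·0.475)) / √(0.45·0.55 + 0.60·0.40)] = Φ[(2.25 − 1.384)/0.698] = Φ(1.24) = 89.3%. It reproduces and has no bearing here. The check itself is textual.

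**Step 1. Follow a silent new stone found on Week 24 imaging.**

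| Step | If the site applies 9.5.1.4.3 to every stone | If the site applies the significance wording of 9.5.1.4.8 |
|---|---|---|
| Adverse event page | Recorded | May not be recorded |
| Urolithiases table by arm (SAP 4.6.2) | Counted | Not counted if not recorded |
| Imaging listing (SAP 4.6.6) | Listed, if the result is in the database | Listed, if the result is in the database |
| By-arm table of imaging results | None planned | None planned |

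**Step 2. Is timing the obstacle?** No. Adverse events are collected through the last visit and for 7 days after the last dose (Protocol 9.5.1.4.1). The treatment-emergent window runs to 28 days after the last dose (SAP 4.6.2). A new Week 24 stone recorded as an adverse event is counted.

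**Step 3. Would another summary pick it up?** Discontinuations are tabulated by primary reason and arm, and nephrolithiasis is a discontinuation criterion. That criterion (Protocol 9.5.5, item 10) leaves out the final visit, which is when the scheduled follow-up imaging takes place in completers.

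**Step 4. Does the wording of 9.5.1.4.8 leave room for a silent stone?** Yes. Its purpose sentence names calculi and clinically significant calculi separately, and its reporting sentence speaks only of clinically significant findings. It neither includes nor excludes the rest.

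**Step 5. Size.** The documents give no stone rate and no fraction of imaging-found stones recorded as adverse events, so the loss cannot be derived. As an illustration on assumed values only, let the true new-stone rates be p₁ and p₂ and let a fraction f be recorded in both arms. Then a = f·p₁, b = f·p₂, the expected counts are 225a and 225b, and the Wald interval is (b − a) ± 1.96·√[a(1−a)/225 + b(1−b)/225].

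For 1% v 5% with f = 1: 0.04 ± 1.96·√[(0.0099 + 0.0475)/225] = 0.04 ± 0.0313, that is 0.87 to 7.13 points.

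| Assumed rates | f | Expected counts | Difference, points (95% CI) |
|---|---|---|---|
| 1% v 3% | 1 | 2.2 v 6.8 | 2.00 (−0.58 to 4.58) |
| 1% v 3% | 0.5 | 1.1 v 3.4 | 1.00 (−0.84 to 2.84) |
| 1% v 5% | 1 | 2.2 v 11.2 | 4.00 (0.87 to 7.13) |
| 1% v 5% | 0.5 | 1.1 v 5.6 | 2.00 (−0.24 to 4.24) |
| 1% v 5% | 0.25 | 0.6 v 2.8 | 1.00 (−0.59 to 2.59) |
| 2% v 8% | 1 | 4.5 v 18.0 | 6.00 (2.01 to 9.99) |
| 2% v 8% | 0.5 | 2.2 v 9.0 | 3.00 (0.13 to 5.87) |

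The Wald interval is rough at counts this small, and 225 per arm is the enrolment target, so the number imaged twice will be lower. The table shows only the direction: partial recording shrinks the visible difference in proportion to f. At 1% v 3% the interval includes 0 even with every stone counted.

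**The case against.** The strongest reply is that the two adverse event passages do not conflict. Section 9.5.1.4.8 does not say that only clinically significant findings are reported. It covers any abnormality on abdominal imaging, in wording close to that for physical examinations in 9.5.1.4.6. Section 9.5.1.4.3 is specific to calculi. Read together, calculi are always adverse events and other imaging findings are reported if significant. Section 9.5.1.4.1 also counts any new disease as an adverse event. On that reading nothing is lost. This stands as a legitimate reading, but no text says which passage governs a silent stone, so the plan does not secure it.

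A reader might infer that stones found by imaging vanish from the report. They do not: the SAP plans a listing that Protocol 9.7.1.8.6 does not call for. Calculi are also asked about at treatment visits (9.1.2, 9.1.3), and suspected calculi prompt an unscheduled visit. What is missing is a by-arm count for stones without symptoms.

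A reader might also infer that the imaging is an unbiased assessment of every subject. The documents do not support that. They describe no central reading, and early discontinuation procedures are completed wherever possible (9.5.5), so some subjects will have no exit image. Nor do the documents give a reason to expect recording to differ by arm, since site staff are blinded (9.4.6).

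Finally, SAP 4.6 specifies no between-arm difference with a confidence interval for any safety outcome. Requiring one here alone would go beyond the plan's approach. That objection is accepted. It does not apply to a simple count.

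**Conclusion.** The point holds in a limited form. Neither document plans an analysis of the imaging, and the only by-arm summary of calculi counts recorded adverse events. The protocol does not settle whether a silent new stone is one of them. The by-arm count can therefore miss such stones; if every site applies 9.5.1.4.3 to every stone, the loss is zero.

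No size can be put on the loss. The illustrative figures rest wholly on assumed stone rates and capture fractions and should not be quoted as a loss of power, because the safety analysis is descriptive. It would also be too strong to say that the two passages flatly contradict each other or that the sponsor has left stones out of the report.

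This is a cheap improvement. The primary analysis and its error control are unaffected.

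**What to change.** 1. In SAP 4.6.6, and in matching words in Protocol 9.7.1.8.6, replace the no-analysis statement for imaging with a descriptive table by arm: number and percentage of subjects with calculi on Week 24 or early termination imaging and none at Screening. The denominator is subjects imaged at both times, with that number shown. A difference with 95% CI is optional and descriptive only.
2. Confirm that presence and absence results, negatives included, are in the database. The planned listing presupposes that imaging data are captured, but Protocol 9.5.1.4.8 names only site source documents.
3. Reconcile Protocol 9.5.1.4.3 and 9.5.1.4.8 so that one rule states which imaging-found calculi are recorded as adverse events.

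The cost is one extra safety table, a check of data capture (more if negatives were not collected) and a clarifying protocol sentence, which needs an amendment or administrative change under Protocol 11.1. No procedure or clinical rule changes. SAP Section 2 allows documented updates before unblinding. Specifying the table by then is better than leaving it to the optional exploratory analyses of SAP 4.8.
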